8.3 OTHER ENDPOINTS

None

8.4 COVARIATES

We will use demographic and clinical information available at the index date and baseline period of the initiation prescription for apixaban, edoxaban, and warfarin cohorts.

Variable	Role	Operational definition
Sex Category	Baseline characteristic	Dichotomous variable equals 1 if sex is male and 2 if female
Age	Baseline characteristic	Age (in years) at the index date
Physician specialty	Baseline characteristic	Dichotomous variable equals 1 if a physician specialty on the index date is categorized into a cardiac specialty and 0 if others. Following specialties will be categorized as the cardiac specialty: cardiology stroke, cardiovascular surgery, pediatric cardiology, neurosurgery, cardiovascular medicine, and neurology. If there are ≥ 1 specialties but including the cardiac specialty, the physician specialty will be regarded as the cardiac specialty.
Hospital size (<500 beds or not)	Baseline characteristic	Dichotomous variable equals 1 if hospital size on the index date is <500 beds and 0 if ≥ 500 beds.
Hospitalization status on index date	Baseline characteristic	Dichotomous variable equals 1 if hospitalization status is inpatient and 0 if outpatient.
CHADS ₂	Baseline characteristic	CHADS ₂ score will be calculated based on age and the presence of congestive heart failure, hypertension, diabetes, and stroke or TIA.

CHA ₂ DS ₂ -VASC	Baseline characteristic	CHA ₂ DS ₂ -VASC score will be calculated based on age and the presence of congestive heart failure, hypertension, diabetes, stroke or TIA, vascular disease and sex category.
PT-INR (Prothrombin time-international normalized ratio)	Baseline period	Continuous variable. * Only available for patients treated with warfarin
Heart failure diagnosis in baseline	Baseline characteristic	Dichotomous variable equals 1 if there are ≥ 1 diagnoses for heart failure ICD-10 or disease codes during the baseline period.
Coronary heart disease diagnosis in baseline	Baseline characteristic	Dichotomous variable equals 1 if there are ≥ 1 diagnoses for coronary heart disease ICD-10 or disease codes during the baseline period.
Peripheral arterial disorder diagnosis in baseline	Baseline characteristic	Dichotomous variable equals 1 if there are ≥ 1 diagnoses for peripheral arterial disorder ICD-10 or disease codes during the baseline period.
Myocardial infarction diagnosis in baseline	Baseline characteristic	Dichotomous variable equals 1 if there are ≥ 1 diagnoses for myocardial infarction ICD-10 or disease codes during the baseline period.
Hyperthyroidism or thyrotoxicosis in baseline	Baseline characteristic	Dichotomous variable equals 1 if there are ≥ 1 diagnoses for hyperthyroidism ICD-10 or disease codes during the baseline period.
Stroke, TIA or SE diagnosis in baseline	Baseline characteristic	Dichotomous variable equals 1 if there are ≥ 1 diagnoses for Stroke, TIA or systemic embolism ICD-10 or disease codes during the baseline period.
Renal dysfunction diagnosis in baseline	Baseline characteristic	Dichotomous variable equals 1 if there are ≥ 1 diagnoses for renal dysfunction ICD-10 or disease codes during the baseline period.
Liver dysfunction diagnosis in baseline	Baseline characteristic	Dichotomous variable equals 1 if there are ≥ 1 diagnoses for liver dysfunction ICD-10 or disease codes during the baseline period.
Bleeding diagnosis in baseline	Baseline characteristic	Dichotomous variable equals 1 if there are ≥ 1 diagnoses for bleeding ICD-10 or disease codes during the baseline period.
Hypertension diagnosis in baseline	Baseline characteristic	Dichotomous variable equals 1 if there are ≥ 1 diagnoses for hyper tension ICD-10 or disease codes during the baseline period.
Diabetes mellitus diagnosis in baseline	Baseline characteristic	Dichotomous variable equals 1 if there are ≥ 1 diagnoses for diabetes mellitus ICD-10 or disease codes during the baseline period.
Cancer diagnosis in baseline	Baseline period	Dichotomous variable equals 1 if there are ≥ 1 diagnoses for diabetes mellitus ICD-10 or disease codes during the baseline period.
Treated with antiplatelet drug in baseline	Baseline characteristic	Dichotomous variable equals 1 if there are ≥ 1 prescriptions of antiplatelet drug ATC or receipt codes during the baseline period.
Treated with NSAIDs in baseline	Baseline characteristic	Dichotomous variable equals 1 if there are ≥ 1 prescriptions of NSAIDs ATC or receipt codes during the baseline period.

Treated with gastric secretion inhibitor in baseline	Baseline characteristic	Dichotomous variable equals 1 if there are ≥ 1 prescriptions of gastric secretion inhibitor drug ATC or receipt codes during the baseline period.
Treated with statin-based drug in baseline	Baseline characteristic	Dichotomous variable equals 1 if there are ≥ 1 prescriptions of statin-based drug ATC or receipt codes during the baseline period.
Treated with anti-hypertensives in baseline	Baseline characteristic	Dichotomous variable equals 1 if there are ≥ 1 prescriptions of anti-hypertensive ATC or receipt codes during the baseline period.
Treated with anti-arrhythmics in baseline	Baseline characteristic	Dichotomous variable equals 1 if there are ≥ 1 prescriptions of anti-arrhythmics ATC or receipt codes during the baseline period.
Treated with beta-blockers in baseline	Baseline characteristic	Dichotomous variable equals 1 if there are ≥ 1 prescriptions of beta-blockers ATC or receipt codes during the baseline period.
Treated with heparins in baseline	Baseline characteristic	Dichotomous variable equals 1 if there are ≥ 1 prescriptions of heparins ATC or receipt codes during the baseline period.
Cardioversion in baseline	Baseline characteristic	Dichotomous variable equals 1 if there is ≥ 1 operation of cardioversion receipt codes during the baseline period.

9 HANDLING OF MISSING VALUES

No imputation for missing data is planned.

10 STATISTICAL METHODOLOGY AND STATISTICAL ANALYSES

10.1 STATISTICAL METHODS

10.1.1 Propensity Score Matching

In this study, matched cohorts (apixaban vs. warfarin, dabigatran versus warfarin, edoxaban vs. warfarin and rivaroxaban versus warfarin) will be created. Propensity scores will be estimated by unconditional logistic regression analyses that incorporate potential predictors of therapy as independent variables in the regression and cohort status as the outcome. The matching between warfarin group and each NOAC group (reference), 1:1 propensity score matching (PSM) method without replacement will be conducted. We will apply nearest neighbour method within caliper (width=0.2 times the standard deviation of the logit of the propensity score) matching technique. Standardized differences will be used to assess the balance of covariate between warfarin group and each NOAC group. If the standardized difference is less than 10%, the covariates are considered balanced. The following covariates will be included in the logistic regression:

- age on index date
- gender

- CHADS₂ score in baseline
- CHA₂DS₂-VASc score in baseline
- heart failure diagnosis in baseline
- coronary heart disease diagnosis in baseline
- peripheral arterial disorder diagnosis in baseline
- myocardial infarction diagnosis in baseline
- hyperthyroidism or thyrotoxicosis in baseline
- TIA diagnosis in baseline
- stroke or SE diagnosis in baseline
- renal dysfunction diagnosis in baseline
- liver dysfunction diagnosis in baseline
- bleeding diagnosis in baseline
- hypertension diagnosis in baseline
- diabetes mellitus diagnosis in baseline
- treated with antiplatelet drug in baseline
- treated with NSAIDs in baseline
- treated with gastric secretion inhibitor in baseline
- treated with statin-based drug in baseline
- treated with anti-hypertensives in baseline
- treated with anti-arrhythmics in baseline
- treated with beta-blockers in baseline
- treated with heparins in baseline
- cardioversion in baseline

The operational definitions for the above covariates are shown in the Section 6.4.

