10.1.2 Inverse probability treatment weighting (IPTW)

As an alternative methods to a simple PSM (shown above), IPTW with stabilized weights will be used as a secondary analysis to balance patient characteristics between two groups⁵⁻⁷.

Propensity score will be calculated by using a multinomial logistic model as mentioned above (see 10.1.1). However, if a treated patient has a very low propensity score, a very large weight can be created. Large weights can increase the variability of estimated treatment effect. In order to address this, the weights can be stabilized. Stabilized weights will be calculated by using a

$$\frac{\sum_{i=1}^{N_T} PS_i}{N_T} * \frac{1}{PS_i}$$

formula shown below, by multiplying the treatment and control weights by a constant, equal to the expected value of being in the treatment or comparison cohorts, respectively.

The distribution of the stabilized weight will be reviewed. If there are extreme outliers, the large weights could be set to a less extreme value (e.g. recoding all weights that are outside 5th and 95th percentile). If needed, truncation can be done after stabilizing the weights. After the weights are applied, the balance of the baseline covariates will be assessed. First, the means and proportions of baseline variables are compared. The standardized difference compares the difference in means in units of the standard deviation. If the standardized difference is less than 10%, the covariates are considered balanced.

For continuous variables, the balance of the distribution is also assessed. The high-order moments and interactions between variables should be similar between treatment groups. The standardized difference is used to compare the mean of the square of continuous variables. Graphical comparisons of the distribution of continuous variables are completed. Side-by-side boxplots and empirical cumulative distribution functions are used to compare the distribution of continuous covariates. The graphical approach can be subjective so a numerical method for comparing the distribution of continuous baseline covariates is also completed. Kolmogorov-Smirnov test allows a comparison of the distribution of a continuous variable between two independent groups.

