10.1.3 Analysis of Time-to-Event Data

Time-to-endpoints will be summarized by OAC with the number and percentage of patients with event, and event rates. Event rates will be calculated as the number of patients with event per 100 patient-years at risk. In addition, total patient-years will be presented for each OAC.

Patients who experience a clinical endpoint event after the earlier of their discontinuation of the index OAC, switching from the index OAC, withdrawal from the database, or the end of intended follow-up period (i.e., two years after the index date as primary and one year for a sensitive analysis) will be censored.

Patients who do not experience a clinical endpoint event will be censored at the earlier of their discontinuation of the index OAC, switching from the index OAC or withdrawal from the database will be censored.

Propensity score matching

See above

Cox proportional hazards model

Cox proportional hazards model will be used to compare endpoints in each of the propensity-score-matched cohorts, with robust sandwich estimates to account for the clustering within matched sets. The Cox proportional hazards model will include only index OAC treatment as the independent variable if patient characteristics are balanced between groups based on standardized difference in components of the PS. If not balanced, the unbalanced variable will be also included to the model in addition to the index OAC treatment. The hazard ratios with corresponding 95% confidence intervals and p-values will be reported.

CCI

Kaplan-Meier Method

For each endpoint, Kaplan-Meier curves will be plotted for the time from the index date to first event by index OAC treatment in each of the propensity-score-matched cohorts. The log-rank test is used for comparison between two curves.

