10.1.4 Analysis of Continuous Data

Continuous data will be summarized using descriptive statistics, including the mean, standard deviation, median, first and third quartiles, and minimum and maximum. Baseline characteristics will be compared between patients treated with warfarin and patients treated with apixaban or

edoxaban using t-test or Mann-Whitney's U test depending on the distribution of the variables. In addition, standardized differences will be calculated for each variable.

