10.1.5 Analysis of Categorical Data

Counts and percentages will be provided for dichotomous and polychotomous variables of baseline patient characteristics when performing descriptive analysis. Standardized differences will be calculated for each variable. For calculation of standardized differences, categorical variables will be converted into a set of binary indicators, one for each non-reference level of the variable and then a set of standardized differences defined⁶. In addition, the counts and percentages will be compared between patients treated with warfarin and patients treated with apixaban or edoxaban using chi-square tests.

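### The propensity score omits index-date hospitalization status, and warfarin starts are not limited by calendar time (which matters mainly for edoxaban), so residual confounding is possible but not shown

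*SAP*

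**What the plan says.** SAP 10.1.1 says the score should hold potential predictors of therapy, then closes the list: "The following covariates will be included in the logistic regression". I count 25 terms, from age to cardioversion. SAP 10.1.2 sends the reader back to 10.1.1 for the IPTW score and gives no list of its own.

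SAP 8.4 also defines index-date hospitalization status ("Dichotomous variable equals 1 if hospitalization status is inpatient and 0 if outpatient"), cancer, physician specialty and hospital size. None is restricted to one drug, unlike PT-INR, and none is on the 10.1.1 list. The cancer row is defined by "diagnoses for diabetes mellitus ICD-10 or disease codes during the baseline period", although Appendix-1 has a separate cancer code list. No calendar-time variable appears in 8.4 or 10.1.1.

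On balance, SAP 10.1.5 promises that "Standardized differences will be calculated for each variable" for categorical baseline characteristics. SAP 10.1.3 keeps treatment as the only Cox term if the groups are "balanced between groups based on standardized difference in components of the PS", and otherwise adds the unbalanced variable. Protocol 7.7 gives balance after matching as its reason for leaving other covariates out.

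The data run from March 2011 to December 2017 (SAP 3). SAP 2 dates the introductions as dabigatran March 2011, rivaroxaban January 2012, apixaban December 2012 and edoxaban September 2014. No visible text limits warfarin index dates to the period when the comparator could be prescribed.

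**The concern.** There are two separate gaps.

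The first is a variable that is measured but not used. Patients started in hospital plausibly differ from outpatients both in drug choice and in bleeding or stroke risk. The plan could display a large standardized difference in inpatient start and still prescribe a treatment-only Cox model, because the trigger looks only inside the score. IPTW is no independent check, since it uses the same list.

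The second is a variable that is never measured. Before September 2014 nobody could start edoxaban, so early warfarin starters have no edoxaban contemporaries. If event rates, coding or care changed over the period, that change would be read as a drug effect, and no planned balance table would show it.

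At stake is a modest shift in hazard ratios tested at two-sided 0.05 with no multiplicity adjustment (SAP 6.2).

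**Working it through.** **The plan's own figure.** The SAP 6.2 sample sizes reproduce. Events = 4(1.96 + 0.84)²/(ln HR)² gives 120, 247 and 631 for HR 0.6, 0.7 and 0.8. For HR 0.7 at 2.1%/year, the two-year control probability is 1 − 0.979² = 4.156%, and the treated probability is 1 − (1 − 0.04156)^0.7 = 2.928%. Then 247/0.07084 = 3,487, against 3,488 printed. The table therefore assumes two years for everyone without dropout, which fits the horizon in SAP 10.1.3 ("two years after the index date as primary and one year for a sensitive analysis"). The point does not depend on this table; it only helps to set event counts below.

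**The lists compared.**

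| Variable | Defined in 8.4 | In the score | Balance tabulated | Imbalance leads to adjustment |
|---|---|---|---|---|
| Hospitalization status | yes | no | yes | no |
| Cancer | yes, with diabetes codes | no | yes | no |
| Physician specialty, hospital size | yes | no | yes | no |
| Index year | no | no | no | no |

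**Hospitalization status.** The documents give no inpatient share by drug and no risk ratio, so both are assumed. Spurious HR when the true HR is 1 = (1 + p_NOAC(RR − 1))/(1 + p_warf(RR − 1)), with p_warf = 50%. Example: (1 + 0.35 × 0.5)/(1 + 0.50 × 0.5) = 1.175/1.25 = 0.94.

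| NOAC inpatient share | Standardized difference | RR 1.5 | RR 2.0 |
|---|---|---|---|
| 35% | 30.7% | 0.94 | 0.90 |
| 40% | 20.2% | 0.96 | 0.93 |
| 42.5% | 15.1% | 0.97 | 0.95 |
| 45% | 10.0% | 0.98 | 0.97 |

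The last two rows also show what remains of the first two if terms already in the score absorb half the gap. With the imbalance reversed, the range is 1.02-1.11.

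**Calendar time.** Assume uniform starts, a full 180-day look-back and introduction on the 1st of the month. The warfarin window is then 28 August 2011 to 31 December 2017, or 2,317 days.

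- Edoxaban: 1,100/2,317 = 47% of the window precedes introduction.
- Apixaban: 461/2,317 = 20%.
- Rivaroxaban: 126/2,317 = 5%.
- Dabigatran: 0%.

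Without the look-back the shares are 51%, 26%, 12% and 0%. The mean start-date gap is half the pre-introduction time: 1,100/2/365.25 = 1.51 years for edoxaban, 0.63 for apixaban and 0.17 for rivaroxaban. With an assumed yearly fall g of 3-5% in event rates, (1 − g)^gap gives 0.93-0.96, 0.97-0.98 and 0.99 or above.

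**Cancer.** Assumed 16% vs 20% with RR 1.5: 1.08/1.10 = 0.98.

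**Effect on the test (edoxaban stroke/SE).** Take 4,438 pairs (the CER2 count in Protocol 7.5) and the 6.2 control rates. The two-year cap and the data cut give mean maximum follow-up of 1.40 years (edoxaban) and 1.68 years (warfarin). Linear events are 4,438 × 0.012 × 3.08 = 164 and 4,438 × 0.026 × 3.08 = 355; allowing for exponential decline, 163 and 348. With shift |ln HR| × √events/2, the false-positive rate is:

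- 5-17% for spurious HR 0.90-0.98 (inpatient start), and 5-8% for 0.95-0.98;
- 6-11% for 0.93-0.96 (calendar time).

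Discontinuation lowers the event counts and hence these rates.

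**The case against.** The strongest reply is that every prevalence, risk ratio and time trend above is assumed, and even the direction is unknown. Heparin, cardioversion, heart failure, prior stroke and prior bleeding are in the score and plausibly stand in for inpatient start. With half the gap absorbed, the false-positive rate is 5-8% against a nominal 5%. Protocol 7.9 already concedes residual confounding. Redacted blocks follow the Cox paragraph and fill much of SAP 10.1.8, and they may hold sensitivity analyses. Choosing covariates is also a judgement: physician specialty and hospital size are equally unscored.

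Most of this limits the size of the point and not its existence. The proxies are baseline-period variables, whereas hospitalization status describes the patient on the day of the choice. The general caveat does not replace adjustment for a variable already in hand. Redacted text cannot be judged, but the visible list and trigger rule are complete as written. The reply on selectivity has some force. I rank hospitalization status first because it speaks to the patient's acute state, while specialty and hospital size describe the provider; that ranking is itself a judgement.

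A reader might infer that an imbalance in calendar time would be seen and ignored. It would not be seen at all, because index year is not an 8.4 variable. A reader might also think an index-year term alone is enough for edoxaban. It is not: before introduction the probability of edoxaban is zero by construction, and IPTW would keep those warfarin starters in the weighted sample.

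**Conclusion.** The gap is real and should be fixed, with medium confidence in its importance. Two facts rest on the text alone. Index-date hospitalization status is defined but left out of the score, and imbalance in it triggers nothing. Calendar time is uncontrolled, which matters chiefly for edoxaban, little for apixaban, and negligibly for rivaroxaban and dabigatran if starts are roughly uniform.

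The illustrative bias is a few per cent, up to about 10% on the hazard ratio. At the plan's own 10% balance limit it is only 2-3%. Cancer is a minor item.

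A reader might infer that the comparisons are biased in favour of the NOACs. The documents do not support that: they give no covariate distribution by drug, and the reverse direction is equally open. Nor do they support a large calendar effect. An early share of 51% with a period risk ratio of 2 would give 1/1.51 = 0.66, but nothing in the documents points to such a change. The rates above concern stroke/SE; the documents give no bleeding rates from which to repeat the calculation.

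**What to change.** 1. Add hospitalization status on the index date to the SAP 10.1.1 list, for both PSM and IPTW. It then becomes part of the score, and the existing 10.1.3 rule covers it in the matched cohorts without new wording.
2. For the edoxaban comparison, restrict warfarin index dates to September 2014 onward and add index year to the score within that period. For apixaban, run the same restriction (from December 2012) as a sensitivity analysis. No calendar change is required for rivaroxaban or dabigatran.
3. Minor: reconcile the 8.4 cancer row with the Appendix-1 list, then add cancer to the score. For physician specialty and hospital size, report standardized differences and run a sensitivity analysis adding them if either exceeds 10%.

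The cost is SAP wording and a rerun of the propensity models. Hospitalization status and cancer codes are held in the database, and index year follows from the index date. Some matched pairs will be lost.

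- Edoxaban, with CER2 counts and uniform starts: the warfarin pool falls from 14,830 to 14,830 × 0.525 = about 7,800, still about 1.75 per edoxaban patient. The ceiling remains 4,438 pairs. That covers the 3,488 needed for HR 0.7 at 2.1%/year if 79% of edoxaban patients are matched. It reaches no HR 0.8 row (smallest 6,817), with or without the restriction.
- Apixaban: the pool would fall to 14,830 × 0.801 = about 11,900. This no longer reaches 14,683 (HR 0.8, 1.2%/year). It reaches 11,031 (1.6%/year) only if 93% of warfarin patients are matched, against 74% unrestricted. That is why the apixaban restriction belongs in a sensitivity analysis.

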10.1.2 Inverse probability treatment weighting (IPTW)

As an alternative methods to a simple PSM (shown above), IPTW with stabilized weights will be used as a secondary analysis to balance patient characteristics between two groups⁵⁻⁷.

Propensity score will be calculated by using a multinomial logistic model as mentioned above (see 10.1.1). However, if a treated patient has a very low propensity score, a very large weight can be created. Large weights can increase the variability of estimated treatment effect. In order to address this, the weights can be stabilized. Stabilized weights will be calculated by using a

$$\frac{\sum_{i=1}^{N_T} PS_i}{N_T} * \frac{1}{PS_i}$$

formula shown below, by multiplying the treatment and control weights by a constant, equal to the expected value of being in the treatment or comparison cohorts, respectively.

The distribution of the stabilized weight will be reviewed. If there are extreme outliers, the large weights could be set to a less extreme value (e.g. recoding all weights that are outside 5th and 95th percentile). If needed, truncation can be done after stabilizing the weights. After the weights are applied, the balance of the baseline covariates will be assessed. First, the means and proportions of baseline variables are compared. The standardized difference compares the difference in means in units of the standard deviation. If the standardized difference is less than 10%, the covariates are considered balanced.

For continuous variables, the balance of the distribution is also assessed. The high-order moments and interactions between variables should be similar between treatment groups. The standardized difference is used to compare the mean of the square of continuous variables. Graphical comparisons of the distribution of continuous variables are completed. Side-by-side boxplots and empirical cumulative distribution functions are used to compare the distribution of continuous covariates. The graphical approach can be subjective so a numerical method for comparing the distribution of continuous baseline covariates is also completed. Kolmogorov-Smirnov test allows a comparison of the distribution of a continuous variable between two independent groups.

